4.8 STUDY DURATION AND WITHDRAWAL CRITERIA

Patients will continue treatment until disease progression or development of unacceptable toxicity. In addition, patients may be discontinued from treatment and/or withdrawn from the study for other reasons, as outlined below. Any subject removed from the trial will remain under medical supervision until discharge or transfer is medically acceptable. In all cases, the reason for withdrawal must be recorded in the appropriate eCRF and in the subject's medical records. Patients will be followed once off-treatment for up to 5 years for overall survival endpoints.

4.8.1 Mandatory Withdrawal Criteria

Subjects **must be withdrawn from the trial** (treatment and procedures) for the following reasons:

- *Subject withdraws consent* from study treatment and study procedures. A subject must be removed from the trial at his/her own request or at the request of his/her legally acceptable representative. At any time during the trial and without giving reasons, a subject may decline to participate further. The subject will not suffer any disadvantage as a result.

- *Pregnancy*. Pregnancy will be reported within the same timelines as an SAE, although a pregnancy per se is not considered an SAE. *NOTE: subjects who have been withdrawn from treatment with study drug because of pregnancy should not undergo CT scans [with contrast]/MRI or bone scans while pregnant.*
- The *investigator concludes* that continuation of the trial would be harmful to the subject's well-being.
- Subject is *lost to follow-up*.
- *Death* occurs.

4.8.2 Possible Withdrawal Criteria

Subjects **may be** withdrawn from the study for any of the following reasons:

- The *subject is non-compliant* with study drug, trial procedures, or both; including the use of anti-cancer therapy not prescribed by the study protocol. Subject compliance with the treatment and protocol includes willingness to comply with all aspects of the protocol, and to have blood collected for all safety evaluations. At the discretion of the investigator, a subject may be discontinued from the trial for non-compliance with follow-up visits or study drug.
- *Severe allergic reaction to regorafenib* (such as exfoliative erythroderma or Grade 3 or 4 hypersensitivity reaction).
- The development of a *second cancer*.
- Development of an *intercurrent illness or situation* which would, in the judgment of the investigator, significantly affect assessments of clinical status and trial endpoints.
- *Deterioration of ECOG performance status* to 4.
- Use of *illicit drugs or other substances* that may, in the opinion of the investigator, have a reasonable chance of contributing to toxicity or otherwise skewing trial result.

5.0 STUDY PROCEDURES

Table 7: Study Visit Parameters

	Baseline (-28days)	On Treatment								Off Treatment	Follow-Up ⁱ	
	Screening ^j	Cycle 1 ^{l, n}				Cycle 2 ^{g, l, n}				Cycle 3+ g, l, n	End of study treatment	
Week	0	1	2	3	4	5	6	7	8	9+		
Regorafenib 160 mg ^e		On			Off	On			Off	Continue ^e		
Informed consent	X											
Medical history ^h	X											
Physical examination	X	X				X				X	X	
Vital signs ^a	X	X	X	X	X	X	X	X	X	X	X	
CBC/Diff	X	X				X				X	X	
PT/INR ^b	X	X ^b				X ^b				X ^b	X ^b	
Clinical chemistry ^c	X	X		X		X		X		X ^c	X	
Pregnancy test ^f	X											
Urine Protein/Creatinine Ratio (UPC)	X											
ECOG PS	X	X				X				X	X	
Disease Measurements ^d	X ^d									X ^d	X ^d	
Study medication dispensing & pill diary collection		X				X				X		
Tolerability/AE reporting	X	X	X	X	X	X				X	X	
Adverse Event Self- Report Survey (AESRS)		X ^k				X				X		
Concomitant medications	X	X				X				X	X	
Phone call ^{m, i}			X ^m	X ^m	X ^m							X ⁱ

- a- Vital signs to include height (height is recorded at screen visit only), weight, blood pressure, pulse, temperature. **Blood pressure should be monitored weekly for the first six weeks of study treatment. A patient blood pressure log will be maintained to aid in monitoring (See Appendices). Patients will record blood pressure at home during the weeks they are not coming to the clinic for exams.**
- b- PT/INR should be closely monitored on day 1 of each cycle.
- c- Electrolytes, calcium, magnesium, BUN, serum creatinine, total bilirubin, AST, ALT, alk phos, albumin, amylase, lipase. Should be done every 2 weeks during Cycles 1 and 2; if no abnormalities are seen, may be done on day 1 only of subsequent cycles. Mid-cycle labs may be performed at a local laboratory if needed to accommodate patient travel logistics..
- d **Imaging should be done as clinically indicated** (i.e. CT, MRI and visual measurements), which satisfy RECIST v 1.1 to evaluate disease (such as in extremity, head and neck). Imaging studies will be done at baseline (within 4 weeks (28 days) before the first dose) and repeated after every 2 cycles of treatment (prior to each odd cycle) for tumor response evaluation.
- ePatients will receive regorafenib daily x 3 weeks followed by 1 week off (1 cycle = 4 weeks).
- f- Women of child-bearing potential must have a negative serum pregnancy test within 7 days prior to registration.
- g- Assessments including physical examination, vital signs, ECOG PS, clinical chemistry, CBC/Diff and PT/INR should immediately precede initiation of the next cycle of therapy. Clinically indicated scans should be performed during the off week immediately preceding initiation of odd numbered cycles.
- h- Medical history findings (i.e. previous diagnoses, diseases or surgeries) will be collected, including those not pertaining to the study indication, beginning before registration, that are considered relevant to the study.
- i- Once off treatment, patients will be followed approximately every 6 months by phone for survival endpoints. Follow-up will continue up to 5 years.
- j- Screening assessments must be completed within 15 days prior to registration, unless otherwise specified. Screening assessments may be used for C1D1 assessments if completed \leq 15 days before study drug initiation.
- k- Adverse Event Self-Report Survey (AESRS) should be disseminated to each patient on day 1 of cycle 1, but no data is collected.
- l- Unless otherwise noted, on-therapy windows for testing will be as follows: imaging scans should be completed within +/- 1 week of the target time point, and labs and physical examination within +/- 3 days of the target time point .
- m- Subjects will be instructed to follow-up weekly with the study team IF they are experiencing any side effects.
- n- Day 1 of each cycle should be every 28 days. In the event that this day falls on a holiday or other such event, study team should use +/- 3 day window to complete pre-treatment procedures, and dispense protocol agents to patients with instructions to commence treatment on day 1. Any missed doses will not be made up and should be skipped to maintain a 28-day cycle.

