
a. According to the National Cancer Institute – Common Terminology Criteria for Adverse Events, version 4.0 (NCI CTCAE v 4.0)
 
b. Excludes alopecia, non-refractory nausea/vomiting, non-refractory hypersensitivity and nonclinical and asymptomatic laboratory abnormalities.
 
c. If no recovery after a 4 week delay*, treatment should be permanently discontinued unless subject is deriving clinical benefit.
 
* Dose modifications are for toxicities except hand-foot-skin reaction, hypertension, and ALT/AST/bilirubin abnormalities. Refer to the tables below for management of these.
			

In addition to these recommended dose modifications, subjects who develop diarrhea, mucositis, anorexia or other events predisposing to fluid loss or inadequate fluid intake should be carefully monitored and rehydrated as clinically necessary. This is in order to minimize the risk of postural hypotension and renal failure.

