4.4.1 Permitted Concomitant Therapies

- Standard therapies for concurrent medical conditions.
- Supportive care for any underlying illness.
- Palliative radiation therapy is allowed if the target lesion(s) are not included within the radiation field and no more than 30% of total bone marrow is irradiated to a total of 20 Gy (EQD2). Protocol treatment should be held 7 days before, during and 7 days after palliative radiation, or at the discretion of the site radiation oncologist. Palliative radiation cannot include target lesions.
- Palliative surgery: Protocol treatment should be held 7 days before and until the wound is healed. If treatment is not resumed within 3 weeks, the case will be reviewed by QAM and PI to determine whether or not subject can restart treatment. Palliative surgery cannot include surgery on target lesions.
- Granulocyte colony-stimulating factor (G-CSF) and other hematopoietic growth factors may be used in the management of acute toxicity, such as febrile neutropenia, when clinically indicated or at the investigator's discretion. However, they may not be substituted for a required dose reduction. Subjects are permitted to take chronic erythropoietin.

- Treatment with nonconventional therapies (such as acupuncture), and vitamin/mineral supplements are permitted provided that they do not interfere with the study endpoints, in the opinion of the investigator.
- Bisphosphonates
- Subjects who are prophylactically treated with an agent such as warfarin or heparin will be allowed to participate. Close monitoring (day 1 of each cycle) is mandatory. *NOTE: Therapeutic doses of anti-coagulants are not permitted.*

4.4.2 Concomitant Therapies Not Permitted:

- Other investigational treatment during study treatment.
- *Prior* use of sorafenib.
- Use of cytotoxic chemotherapy within 21 days of registration.
- Use of targeted therapy within two half-lives of registration.
- Radiation directed at target lesion within 28 days of registration.
- Concurrent systemic antitumor therapy, including cytotoxic therapy, signal transduction inhibitors, immunotherapy, and hormonal therapy.
- Bone marrow transplant or stem cell rescue.

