6.2 PRIMARY ENDPOINT ASSESSMENT

The primary endpoint of the study will be progression-free survival (PFS) at 4 months, defined as the absence of progression at 4 months. Patients must complete at least 2 cycles of study treatment to be considered evaluable for this endpoint.

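### Scans are timed by treatment cycle, and the plan does not settle whether a toxicity delay moves the cycle, so the second scan could fall after the 4-month landmark

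*Combined protocol and SAP*

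**What the plan says.** **Scan timing.** Section 5.0, Table 7 footnote d, has imaging "repeated after every 2 cycles of treatment (prior to each odd cycle) for tumor response evaluation". Footnote g adds: "Clinically indicated scans should be performed during the off week immediately preceding initiation of odd numbered cycles". Footnote l allows a window: "imaging scans should be completed within +/- 1 week of the target time point".

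**Cycle clock.** Footnote n says "Day 1 of each cycle should be every 28 days" and "Any missed doses will not be made up and should be skipped to maintain a 28-day cycle".

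**Delays.** In Section 4.3.1, Table 2 contrasts treating on time with delaying until recovery. Its footnote c reads: "If no recovery after a 4 week delay*, treatment should be permanently discontinued unless subject is deriving clinical benefit". Table 4 (hand-foot-skin reaction) and Table 5 (hypertension) each tolerate a delay of up to 4 weeks. Section 4.4.1 adds: "Protocol treatment should be held 7 days before, during and 7 days after palliative radiation", and the same sentence then lets the site radiation oncologist decide otherwise.

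**Endpoint.** Section 6.2 describes PFS at 4 months as "defined as the absence of progression at 4 months". It gives no landmark in days, no assessment window, and no classification for a patient whose nearest scan is late or missing.

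**The concern.** The endpoint runs on calendar time and the scans run on cycles. The two stay aligned only if cycles keep to the calendar. Footnote n says they do. The delay wording in the dose tables can be read as postponing the start of the next cycle, and footnote g ties the scan to that start. No section says whether a toxicity delay moves day 1, or whether a wholly skipped cycle counts toward the two cycles between scans. Sites could reasonably differ.

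Where day 1 does slide, the only scheduled scan near the landmark moves later, and it does so in patients with toxicity. A progression that occurs before 4 months may then first be seen after 4 months. If that patient is counted as progression-free at 4 months, the error can only favour the drug. With 31 patients and a cut-off of 10 or 11 successes, one or two such patients could change the conclusion.

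**Working it through.** **1. The plan's own design figures (Section 9.3).** Inputs: n1 = 12, R1 = 3, N = 31, R = 10, P0 = 0.22, P1 = 0.45.

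- PET = P(X1 ≤ 3 | 12, 0.22) = 0.739.
- Average N = 12 + (1 - 0.739) × 19 = 16.96.
- Rejection probability = Σ over x = 4 to 12 of P(X1 = x) × P(X2 ≥ 11 - x), with X2 binomial on 19 patients. This gives 0.0468 at 0.22 and 0.8117 at 0.45, so beta = 0.188.

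The tabulated row is reproduced. The Section 9.3 text rejects only above 11 of 31, which gives 0.022 at 0.22. That mismatch is a separate issue, so both rules are carried below.

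**2. Timeline with no drift (day 1 = first dose).**

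- Off week of cycle 4: days 3 × 28 + 22 = 106 to 4 × 28 = 112.
- Latest scan within the window: 112 + 7 = day 119.
- Landmark: 4 × 365.25 / 12 = 121.75 days.

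If footnote n governs, the second scan always precedes the landmark.

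**3. Timeline if day 1 slides.**

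- From day 112: 121.75 - 112 = 9.75, so 10 days of drift passes the landmark.
- From day 119: 121.75 - 119 = 2.75, so 3 days is enough.
- A 28-day drift puts the scan on days 134-140, or 127-147 with the window.

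**4. Conditional effect on type I error.** Assumptions, none of them from the documents: exponential PFS, S(t) = 0.22^(t/121.75); progression found only at scans; a share f of patients whose second scan drifts past the landmark and who are then judged on their first scan; all other patients counted at the true rate of 0.22.

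- If the delay comes after an on-time first scan: S(56) = 0.498.
- If a 4-week delay came earlier and moved the first scan too: S(84) = 0.352.

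Observed rate = (1 - f) × 0.22 + f × S. For example, with f = 0.1 it is 0.198 + 0.050 = 0.248 (late delay) or 0.198 + 0.035 = 0.233 (early delay).

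| Share drifting | Observed rate (early to late delay) | Type I error, R = 10 | Type I error, more than 11 |
|---|---|---|---|
| 0 | 0.220 | 0.047 | 0.022 |
| 10% | 0.233 to 0.248 | 0.067 to 0.096 | 0.034 to 0.052 |
| 20% | 0.246 to 0.276 | 0.093 to 0.169 | 0.049 to 0.102 |

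**5. A gap that exists without any delay.** An on-time scan on day 112 reads status about 10 days before 4 calendar months. Under the same model S(112) = 0.248. If day-112 status stands in for 4 months, type I error is about 0.097 (R = 10) or 0.052 (more than 11). Moving scans to calendar weeks does not remove this. Only the landmark definition in Section 6.2 can.

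**The case against.** The strongest reply is that footnote n already fixes the calendar. Read as written, an interruption costs doses and leaves the scan date alone. Much of the dose-table wording fits that reading: the Table 2 column is headed as a dose interruption, and Tables 4, 5 and 6 speak of interrupting or holding drug. None of them says that day 1 moves. This stands, and it means drift is a possible reading rather than the stated plan. It does not settle the matter, because Table 2 still sets treating on time against delaying, and footnote g still ties the scan to the start of the next cycle.

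A reader might infer that a patient who fails before 4 months but is scanned late is counted as progression-free. Section 6.2 does not say so. With no rule, such a patient could be a success, a failure or not evaluable.

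A reader might also take the radiation hold as a fixed minimum of two weeks. The discretion clause in Section 4.4.1 rules that out.

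Finally, progression can be found between scans. Footnote d also refers to imaging as clinically indicated, physical examination is scheduled each cycle, and Section 6.1.1 allows caliper measurement of superficial lesions. Any such detection lowers the figures above.

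**Conclusion.** The plan contains an unresolved conflict over scan timing, and Section 6.2 has no rule for a late or missing landmark scan. Together they leave room for a toxicity-dependent error in the primary endpoint, which would favour the drug if late-detected failures are counted as successes.

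The documents do not support the stronger statement that delays do push the second scan past 4 months and do turn failures into successes. Under footnote n the scan is done by day 119.

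The size is conditional. With 10-20% of patients drifting, type I error would be roughly 0.07-0.17 against 0.047 under R = 10, and roughly 0.03-0.10 against 0.022 under the text rule. These ranges rest on the exponential shape, the assumed shares and no detection between scans. The documents give no frequency of delay. The colorectal trial summarised in Section 1.3.2 had grade 3 or higher hand-foot skin reaction in 17%, which makes delays foreseeable but is not a delay rate for this trial.

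Severity: a cheap improvement, not a must-fix.

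**What to change.** - **Table 7 footnotes d and g:** schedule tumour assessments at weeks 8, 16 and 24 from first dose and every 8 weeks after that, each within 1 week either side, regardless of dose delays, interruptions or cycle number. This replaces the link to odd-numbered cycles. The week-16 scan is then due by day 119 in every patient.
- **Section 6.2:** state the landmark in days so that it matches the week-16 scan, name that scan with its window as the landmark assessment, and say how a late or missing landmark scan is classified. If the landmark is set at week 16 rather than 4 calendar months, confirm that P0 = 0.22 is meant for that time (step 5 of the working).
- **Footnote n and Tables 2, 4 and 5:** reconcile the delay wording with the 28-day cycle for the purpose of scan timing. No dosing rule needs to change.

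The cost is two amended footnotes and a few sentences in Section 6.2. The number of scans is essentially unchanged. The one downside is that in a delayed patient a scan may not coincide with a cycle visit.

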Treatment Plan	Patients will be treated with regorafenib 160 mg PO daily for the first 3 weeks of each cycle (1 cycle = 4 weeks) until disease progression. Response evaluation will be every 2 cycles (approximately 2 months) using RECIST v 1.1.
Plan for statistical analysis	Optimal two-stage Simon design. First stage includes 12 patients. If > 3 patients have PFS > 4 months, and additional 19 will be enrolled for a total of 31 patients.

SCHEMA

[figure not shown]

TABLE OF CONTENTS

Synopsis	2
Schema	3
Table of Contents	4
List of Abbreviations	5
1.0 Introduction	6
2.0 Study Objectives	9
3.0 Selection of Subjects	9
4.0 Treatment Plan	12
5.0 Study Procedures	23
6.0 Endpoint Assessment	25
7.0 Adverse Events and Safety Monitoring	28
8.0 Drug Information	33
9.0 Statistical Methods and Determination of Sample Size	34
10.0 Study Management	35
Appendices	
References	40

LIST OF ABBREVIATIONS

ALT	Alanine aminotransferase
aPTT	Activated partial thromboplastin time
AST	Aspartate aminotransferase
BUN	Blood Urea Nitrogen
CR	Complete Response
CTCAE	Common Terminology Criteria for Adverse Events
ECOG	Eastern Cooperative Oncology Group
ERK	Extracellular Signal-regulated Kinases
FDA	Food and Drug Administration
FGFR	Fibroblast Growth Factor Receptor
GCP	Good Clinical Practice
GMP	Good Manufacturing Practice
HFSR	Hand-foot-skin reaction
IB	Investigator's Brochure
ICF	Informed Consent Form
ICH	International Conference on Harmonisation
IRB	Institutional Review Board
MAPK	Mitogen Activated Protein Kinase
PD	Progressive Disease
PDGFR- β	Platelet Derived Growth Factor Receptor-beta
PFS	Progression-free survival
PO	per oris , oral
PR	Partial Response
PS	Performance Status
PT/INR	Prothrombin time/ International Normalized Ratio
QD	quaque die , once daily
RAF	Rapidly Accelerated Fibrosarcoma
RAS	Rat sarcoma
RECIST	Response Evaluation Criteria for Solid Tumors
SAE	Serious Adverse Event
SD	Stable Disease
TK	Tyrosine Kinase
TTP	Time to Progression
VEGF	Vascular Endothelial Growth Factor
VEGFR	Vascular Endothelial Growth Factor Receptor

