9.3 TRIAL DESIGN AND DETERMINATION OF SAMPLE SIZE

A two-stage optimal Simon design will be employed to test the null hypothesis that the probability of progression-free survival of 4 months or greater (P) is ≤ 0.22 versus the alternative that the probability ≥ 0.45 . To test this hypothesis with adequate power, a first stage involving 12 patients will be completed. If > 3 patients achieve progression-free survival of 4 months, the trial will be continued for a total of 31 patients. If > 11 out of 31 patients achieve progression-free survival of 4 months, the trial will reject the hypothesis that $P \leq 0.22$ and conclude that $P > 0.45$,

To determine sample size, the following parameters were employed: $P0 = 0.22$, $P1 = 0.45$, $\alpha = 0.05$ and $\beta = 0.20$. Computations originally performed using software PASS (www.ncss.com).

N1	R1	PET	N	R	Avg N	α	β	Satisfied
26	9	0.000	26	9	26.00	0.043	0.194	Single Stage
7	0	0.176	26	9	22.66	0.042	0.199	Minimax
12	3	0.739	31	10	16.96	0.047	0.188	Optimum

Definitions:

N1 – sample size in the first stage

R1 – drug rejection number in the first stage

PET – probability of early termination of study

N – combined sample size of both stages

R – combined drug rejection number after both stages

Avg N – average sample size if this design is repeated many times

α – probability of rejecting that $P < P0$ when this is true

β – probability of rejecting that $P > P1$ when this is true

P0 – response proportion P of a poor drug

P1 – response proportion P of a good drug

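### No planned scan observes the 4-month primary endpoint, the deciding assessment is not named, and the Simon rule may be testing about a 3.5-month rate against a 4-month null

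*Combined protocol and SAP*

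**What the plan says.** **Scan calendar (5.0, Table 7 footnotes).** Footnote n fixes the cycle: "Day 1 of each cycle should be every 28 days", and "Any missed doses will not be made up and should be skipped to maintain a 28-day cycle". Footnote d has imaging "repeated after every 2 cycles of treatment (prior to each odd cycle) for tumor response evaluation". Footnote g places it within the cycle: "Clinically indicated scans should be performed during the off week immediately preceding initiation of odd numbered cycles". Footnote l allows a window: "imaging scans should be completed within +/- 1 week of the target time point". Footnote d also allows imaging as clinically indicated.

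**Months and cycles (Synopsis, Treatment Plan).** "Response evaluation will be every 2 cycles (approximately 2 months) using RECIST v 1.1".

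**Primary endpoint (6.2).** PFS at 4 months, "defined as the absence of progression at 4 months". No scan, window or scoring rule is attached to it.

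**Test (9.3).** The hypotheses concern the chance of remaining progression-free for 4 months or longer: P0 = 0.22 against P1 = 0.45. The optimum design in the table is 12 then 31 patients, R1 = 3, R = 10, alpha 0.047, beta 0.188, early termination 0.739. The text of 9.3 requires more than 11 of 31, whereas R = 10 means more than 10.

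**The concern.** The go/no-go counts at 12 and 31 patients depend on each patient's status at 4 months, but the calendar has no scan at or just after that time, even for a patient with no delays. Someone clear before cycle 5 who progresses in the following days may first be seen to have progressed at about 5.4 months. If progression is dated when documented, that patient counts as a 4-month success.

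The success rate would then be that of an earlier time point, while P0 and P1 are stated for 4 months. An inactive drug would pass more often than the stated alpha, and the reported 4-month PFS would describe roughly weeks 15-16. Because the deciding scan is not named, the analysis could also be scored in other ways with very different error rates.

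**Working it through.** **1. Calendar, in days after first dose.** Cycle 4 starts on day 84 and its off week is cycle days 22-28, so the pre-cycle-5 scan is on days 84 + 21 = 105 to 84 + 27 = 111. With ±7 days this becomes 98-118. Four calendar months is 120-123 days (mean 4 × 30.4375 = 121.75). The scheduled scan is therefore 120 − 111 = 9 to 123 − 105 = 18 days early, and the latest in-window scan still precedes the landmark. The pre-cycle-7 scan is on days 161-167, or 5.29-5.49 months. The pre-cycle-5 scan is at 105/30.4375 = 3.45 to 111/30.4375 = 3.65 months.

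**2. The plan's own figures.** The chance of declaring success at true rate p is

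Σ over x = 4..12 of Bin(x; 12, p) × P[Bin(19, p) ≥ R + 1 − x].

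At p = 0.22 with R = 10 this gives 0.0468; at p = 0.45 it gives 0.812 (beta 0.188). Early termination at 0.22 is 0.739. All match the table in 9.3. The text's cut-off (R = 11) gives alpha 0.022 and power 0.752 before any timing question arises.

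**3. Null rate at the scan.** Assume that 0.22 is a true 4-month rate, that the hazard is constant (9.4 names the exponential) and that only scans detect progression. Then p(t) = 0.22^(t/121.75).

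| Scan day | Scored null rate | Type I error, R = 10 | Type I error, more than 11 |
|---|---|---|---|
| 105 | 0.271 | 0.155 | 0.092 |
| 108 | 0.261 | 0.127 | 0.073 |
| 111 | 0.251 | 0.104 | 0.057 |
| 118 (window limit) | 0.231 | 0.063 | 0.031 |

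At day 108, the chance of stopping after stage 1 under the null falls from 0.739 to 0.614.

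**4. Other readings, all with 0.22 as the null at the landmark.**

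- Half of the progressions between day 108 and 4 months are caught clinically: p = 0.22 + 0.5 × (0.261 − 0.22) = 0.2405, giving 0.081 (R = 10) or 0.042 (more than 11). If all are caught, the result is 0.047 or 0.022.
- Four months means 4 cycles (112 days): p = 0.22^(t/112) for t = 105-111, or 0.242-0.223, giving 0.083-0.051 or 0.044-0.024.
- Success requires a clear pre-cycle-7 scan: p = 0.135-0.125, giving about 0.001 (R = 10). The alternative rate falls to 0.348-0.334 and power to 0.45-0.39 (0.42 at day 164).
- Non-constant hazard (Weibull shape 0.7 to 2, an assumption), scan-only detection, days 105-111: 0.083-0.348 (R = 10) or 0.044-0.248 (more than 11).

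**The case against.** A reader might infer that the true alpha is simply no longer 0.047 and that the success counts are inflated. The documents do not support that as a fact, for five reasons.

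- **No scoring rule is written.** Inflation follows if the pre-cycle-5 scan decides. If a clear scan after 4 months is required, the test is conservative and loses power. The direction is open.
- **The protocol counts in cycle-months.** The Synopsis treats 2 cycles as about 2 months. On that reading the scan is only 1-7 days early, and alpha under the text's cut-off stays below 0.05.
- **Surveillance is not by scheduled scan alone.** Imaging as clinically indicated is allowed, caliper measurement is accepted (6.1.1), a physical examination precedes each cycle (so one falls near day 112), and PFS in 6.3 counts deaths.
- **The origin of 0.22 is not given.** If it came from studies scanned on a similar grid, the null carries much the same shift. It also sits uneasily with 9.1: a 3-month median under constant hazard gives 0.5^(4/3) = 0.40 at 4 months. The recomputed alphas are illustrations, not established operating characteristics.
- **The cut-off is itself unsettled.** The 0.047 belongs to R = 10. Under the text's cut-off, alpha exceeds 0.05 in the constant-hazard scenarios above only with calendar months, an off-week scan and little off-schedule detection.

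All five stand as limits on the size and direction. None removes the mismatch: the calendar arithmetic is not in dispute, the window does not reach day 120, and the sections that define and test the endpoint do not name the assessment that decides it.

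**Conclusion.** The point holds as a mismatch between the scan calendar and the landmark, together with a missing scoring rule. For a patient on schedule, 4-month status is not observed by any planned assessment.

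The effect on type I error is conditional. If progression is dated when documented, months are calendar months, 0.22 is a true 4-month rate, the hazard is constant and only scans detect progression, alpha could be about 0.10-0.16 (R = 10) or 0.06-0.09 (more than 11). With partial clinical detection or cycle-months, the inflation is modest under R = 10, and alpha stays below 0.05 under the text's cut-off. Because the scenarios in the documents' reach run from about 0.001 to about 0.16 under constant hazard, the stated 0.047 cannot be relied on until the deciding assessment is written down.

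**What to change.** In 6.2 and 9.3:

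1. Define the primary endpoint as alive and progression-free at the pre-cycle-5 (week 15-16) assessment. Give its window, and say how progression found off schedule is scored.
2. State P0 and P1 for that same time, with the source of P0 and the scan schedule behind it.
3. Re-derive and restate the cut-off, alpha and power, and reconcile the more-than-10 (table) and more-than-11 (text) rules in the same revision.

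As an example, a day-108 assessment under constant hazard turns 0.22 and 0.45 into 0.22^(108/121.75) = 0.261 and 0.45^(108/121.75) = 0.492. Keeping 12/31 and R1 = 3 with R = 12 (success if more than 12 of 31) gives alpha 0.036 and power 0.81. Across days 105-111, power is 0.83-0.78, so the day used for the calculation should match the window chosen.

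The cost is wording, one recalculation and a slightly higher cut-off, with no added patients or scans. Moving the scan past month 4 is not proposed: it would fall after cycle 5 begins, which conflicts with footnotes d and g and bears on treatment continuation.
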